### **1.3. Schedule of Activities (SoA)**

This SoA shows visits and procedures unique to the intervention-specific appendix (ISA) H0P-MC-BP03 (BP03) for LY3556050. Please refer to master protocol and the CLBP DSA SoAs for additional information.

H0P-MC-BP03 ISA	Randomization	Double-Blind Treatment				Early Discontinuation	Notes
Visit Number	V3	V4	V5	V6	V7	ED	
Study Week	0	2	4	6	8		
Visit Window (days)		±3	±3	±3	±3		
Telephone Visit	X a,b						Visit window +2 days There will be 2 telephone visits between Visit 3 and Visit 4: a Visit occurs 4 days after Visit 3 CCI b Visit occurs 8 days after Visit 3 CCI
Procedures							
Evaluate all I/E criteria	X						
Physical examination	X	X	X	X	X	X	V3-V7: Do symptom-directed physical examination
ECG	X	X	X	X	X	X	V3, V5, and V7: Single ECG before in-clinic dosing and at 3 hours after dosing V4, V6 and ED: Single ECG ECG includes collection of PR interval, QRS duration and interval, and heart rate.
Vital signs	X	X	X	X	X	X	Blood Pressure and Pulse Rate V3, V5, and V7: Collect blood pressure and pulse in supine and standing position before in-clinic dosing and at 3 hours after dosing V4, V6, and ED: Collect blood pressure once  Collect orthostatic blood pressure after 5 minutes supine and then 2-3 minutes after standing and collect pulse after supine and standing blood pressure. Temperature and Respiratory Rate Collect once at each visit
Study intervention	X	X	X	X	X		Intervention is taken orally, twice daily, approximately every 12 hours. V3, V5, and V7: Participants take the morning dose in the clinic. Refer to Section 6.6 for dose titration scheme.

H0P-MC-BP03 ISA	Randomization	Double-Blind Treatment				Early Discontinuation	Notes
Visit Number	V3	V4	V5	V6	V7	ED	
Study Week	0	2	4	6	8		
Visit Window (days)		±3	±3	±3	±3		
Telephone Visit	X a,b						Visit window +2 days There will be 2 telephone visits between Visit 3 and Visit 4: a Visit occurs 4 days after Visit 3 CCI [REDACTED] [REDACTED] b Visit occurs 8 days after Visit 3 CCI [REDACTED] [REDACTED].
Procedures							
Intervention compliance		X	X	X	X	X	
Laboratory Tests and Sample Collection							
Hematology	X	X	X	X	X	X	V3: Collect laboratory tests before dosing.
Chemistry	X	X	X	X	X	X	V3: Collect laboratory tests before dosing.
Urine drug screen							Performed at investigator discretion.
Serum pregnancy		X	X	X	X	X	For WOCBP only

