Urine pregnancy	X						For WOCBP only Collect sample within 24 hours prior to first dose.
Lipid panel	X	X	X	X	X	X	
Thyroid panel	X	X	X	X	X	X	
Cystatin C	X	X	X	X	X	X	
HbA1c					X	X	

H0P-MC-BP03 ISA	Randomization	Double-Blind Treatment				Early Discontinuation	Notes
Visit Number	V3	V4	V5	V6	V7	ED	
Study Week	0	2	4	6	8		
Visit Window (days)		±3	±3	±3	±3		
Telephone Visit	X a,b						Visit window +2 days There will be 2 telephone visits between Visit 3 and Visit 4: a Visit occurs 4 days after Visit 3 CCI b Visit occurs 8 days after Visit 3 CCI
Procedures							
PK sample	X	X	X	X	X	X	V3: Collect at 3 hours ±15 minutes after dosing.  V5 and V7: Collect samples before dosing and at 3 hours ±15 minutes after dosing.  V4, V6, and ED: Collect single sample at any time.  Record date and time of collection.
Somatostatin-regulated hormone sample	X	X	X	X	X	X	
CCI							
Participant Device							
Participant returns device					X	X	CCI

Abbreviations: ECG = electrocardiogram; ED = early discontinuation; HbA1c = glycated hemoglobin; I/E = inclusion and exclusion; ISA = intervention-specific appendix; PK = pharmacokinetic; V = visit; WOCBP = women of childbearing potential.

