##### **Visit 3**

At Visit 3 post randomization

- the site completes the BP03 baseline procedures and sample collection,
- participants receive their first dose of study intervention and instructions for dosing at home,
- the site completes all posttreatment sample collection and safety monitoring, and
- the site instructs participants to continue with study restrictions and Numeric Rating Scale (NRS) diary entries before their visit discharge.

CCI

CCI

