## 10. Supporting Documentation and Operational Considerations

### 10.1. Appendix 1: Clinical Laboratory Tests

The master protocol describes tests that may be performed at additional times noted in the SoA for this ISA. This table describes tests unique for this ISA.

Chemistry	Additional Thyroid Tests	Other SST-Regulated Hormones	Other Tests
Cystatin-C	Free Triiodothyronine (FreeT3)	Growth hormone	Amylase
TSH	Total Triiodothyronine (T3)	Insulin-like Growth Factor-1 (IGF-1)	Lipase
	Free Thyroxine (FreeT4)	Prolactin	LY3556050 concentration
	Total Thyroxine (T4)	Gastrin	Serum pregnancy test
		Glucagon	HbA1c
		Insulin	

Abbreviations: HbA1c = glycated hemoglobin; SST = somatostatin; TSH = thyroid-stimulating hormone.

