#### *Participation in the Study*

Women not of childbearing potential and of childbearing potential may participate in this study.

Women not of childbearing potential include those who

- have a congenital anomaly such as Müllerian agenesis
- are infertile due to surgical sterilization, or
- are postmenopausal.

At least 6 weeks must have passed after surgical bilateral oophorectomy with or without hysterectomy, or after tubal ligation.

Women of childbearing potential must test negative for pregnancy prior to initiation of treatment as indicated by a negative serum pregnancy test at the screening visit followed by a negative urine pregnancy test within 24 hours prior to exposure.

Women of childbearing potential who are completely abstinent or in a same-sex relationship, as part of their preferred and usual lifestyle, must agree to either remain abstinent or stay in a same-sex relationship without sexual relationships with males.

All other WOCBP must agree to use 1 highly effective method of contraception (less than 1% failure rate), or a combination of 2 effective methods of contraception, for the entirety of the study.

Abstinence or contraception must continue for 3 days after the last dose of intervention.

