6.12.4. Vital Signs and Other Physical Findings

The analysis of vital sign parameters is described in the H0P-MC-CPMP SAP Version 5. Supine, standing, and orthostatic vital signs data will be summarized by treatment, together with changes from baseline, where the baseline is defined as Visit 3 predose assessment. Figures of mean vital signs and mean changes from baseline profiles will be presented by treatment. Additional categorical criteria for abnormal treatment-emergent blood pressure and pulse measurement for adults in BP03 are:

Parameter	Criteria
Orthostatic hypotension (Orthostatic Systolic BP, in mmHg)	Decrease in systolic BP when going from 5 minutes supine to 2-3 minutes standing of ≥ 20 mm Hg
Orthostatic hypotension (Orthostatic Diastolic BP, in mmHg)	Decrease in diastolic BP when going from 5 minutes supine to 2-3 minutes standing of ≥ 10 mm Hg
Orthostatic Pulse Rate (Postural Orthostatic Tachycardia, in bpm)	Increase in pulse when going from 5 minutes supine to 2-3 minutes standing of ≥ 30

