6.17. Totality of Evidence for Safety

The totality of evidence for safety analysis has been briefly described in the H0P-MC-CPMP SAP Version 5. The key safety events to be considered for H0P-MC-BP03 are listed below by domain:

General Adverse Event Information

- Serious adverse events related to study treatment
- Study discontinuation due to adverse event
- Treatment discontinuation due to adverse event
- Treatment discontinuation due to gastrointestinal disorders
- Treatment discontinuation due to potential nervous system disorder.

Cardiovascular

- QTc prolongation: >60 msec increase
- Serious cardiac disorders adverse event
- Cardiac Failure
- Arrhythmia Event
- MACE
- Hypotension event.

Liver function

- Hy's Law case: Serum total bilirubin ≥ 2 and ALT ≥ 3 for at least one visit during the double-blind treatment period.

Metabolic function

- Serious hypoglycemia adverse event
- Treatment-emergent HbA1c: Shift from low/normal at baseline to high at least once during the double-blind treatment period.

Renal function

- Treatment-emergent abnormal eGFR based on Cystatin C: Shifts
 - Mild at baseline to moderate/severe during the double-blind treatment period
 - Moderate at baseline to severe during the double-blind treatment period
- Serious renal event.

Thyroid

- Hypothyroidism.

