Appendix 1. Planned Laboratory Analytes and Direction of Interest

The H0P-MC-CPMP SAP Version 5 describes tests that may be performed broadly for the Chronic Pain Master Protocol. This table describes tests unique to H0P-MC-BP03.

Chemistry	Additional Thyroid Tests	Other SST-Regulated Hormones	Other Tests
Cystatin-C	Free Triiodothyronine (FreeT3)	Growth hormone	Amylase
TSH	Total Triiodothyronine (T3)	Insulin-like Growth Factor-1 (IGF-1)	Lipase
	Free Thyroxine (FreeT4)	Prolactin	LY3556050 concentration
	Total Thyroxine (T4)	Gastrin	Serum pregnancy test
		Glucagon	HbA1c
		Insulin	

Abbreviations: HbA1c = glycated hemoglobin; SST = somatostatin; TSH = thyroid-stimulating hormone.

Thyroid Safety Follow-Up

TSH
Free Triiodothyronine (FreeT3)
Total Triiodothyronine (T3)
Free Thyroxine (FreeT4)
Total Thyroxine (T4)
Thyroglobulin
Anti-Thyroglobulin
Anti-Thyroperoxidase Antibodies
Iodine

Abbreviation: TSH = thyroid-stimulating hormone.

Signature Page for VV-CLIN-020674 v1.0

Approval

PPD

Signature Page for VV-CLIN-020674 v1.0

Approved on 04 Mar 2022 GMT

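### Does the HbA1c shift event in SAP 6.17 lack a baseline, given that the BP03 schedule draws no HbA1c at Visit 3?

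*SAP*

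**What the plan says.** SAP 6.17 lists the safety events that feed the totality-of-evidence assessment, grouped by domain. The metabolic domain has two: a serious hypoglycemia adverse event and "Treatment-emergent HbA1c: Shift from low/normal at baseline to high at least once during the double-blind treatment period". No visit is given for the baseline.

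The BP03 Schedule of Activities in Protocol 1.3 runs from Visit 3 to Visit 7 plus early discontinuation (ED). HbA1c is marked at Visit 7 and ED. The same section limits the table to what is particular to this intervention-specific appendix (ISA) and adds: "Please refer to master protocol and the CLBP DSA SoAs for additional information".

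Protocol 4.1 says that at Visit 3, after randomization, "the site completes the BP03 baseline procedures and sample collection". The one baseline visit spelled out in the readable safety text of the SAP is in 6.12.4, for vital signs: "where the baseline is defined as Visit 3 predose assessment".

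Both laboratory appendices list HbA1c under other tests. Protocol Appendix 1 introduces its table with "This table describes tests unique for this ISA", and SAP Appendix 1 with "This table describes tests unique to H0P-MC-BP03".

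**The concern.** A shift from low or normal to high needs a value from before the first dose. If BP03 baseline samples are those taken at Visit 3, and HbA1c is not among them, a programmer who applies a Visit 3 rule finds nothing to shift from. The appendices strengthen the suspicion. If HbA1c really belongs to this ISA alone, no other schedule would be expected to supply it.

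The stake would be real, though confined to safety. The BP03 schedule normally yields one HbA1c per participant after dosing, at Visit 7 or ED. Without an earlier value, a high result cannot be separated into new and pre-existing. The other metabolic event concerns low glucose, so within that domain the HbA1c shift is the only event that can register a rise in glycaemia, in a trial that also samples insulin and glucagon.

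**Working it through.** No stated figure has to be reproduced. The check compares the schedule, cell by cell, with what each event needs, and then asks what a blank Visit 3 cell can prove.

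**Events in SAP 6.17.** General 5 + cardiovascular 6 + liver 1 + metabolic 2 + renal 2 + thyroid 1 = 17. Three are defined against an earlier value: the QTc increase above 60 msec, the cystatin C eGFR shift and the HbA1c shift. None of the three names its baseline visit.

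**Marks in the BP03 schedule (Protocol 1.3).**

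| Row | V3 | V4 | V5 | V6 | V7 | ED | Marks |
|---|---|---|---|---|---|---|---|
| ECG | X | X | X | X | X | X | 6 |
| Cystatin C | X | X | X | X | X | X | 6 |
| Hematology, chemistry, lipid, thyroid (each) | X | X | X | X | X | X | 6 |
| HbA1c | | | | | X | X | 2 |
| Serum pregnancy | | X | X | X | X | X | 5 |

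So the reading is right: a Visit 3 value is scheduled for the QTc and eGFR events but not for HbA1c.

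**What the blank cell shows.** It shows only that BP03 adds no HbA1c at Visit 3.

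1. The table has no column for Visit 1 or Visit 2, yet exclusion criteria 2027 to 2030 (Protocol 5.2) need QRS, PR, heart rate and eGFR at those visits. Screening data are therefore collected under schedules outside this table.
2. The serum pregnancy row is also blank at Visit 3, and the test sits in the same appendix column as HbA1c. Protocol Appendix 2 nonetheless requires "a negative serum pregnancy test at the screening visit". Neither a blank Visit 3 cell nor the appendix label rules out an earlier value.
3. Protocol Appendix 1 opens by allowing tests from the master protocol to be repeated at extra times given in the ISA schedule. Marks at Visit 7 and ED alone fit that reading: a closing measurement added to one taken at screening. This is an inference and is not stated.

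**Whether a Visit 3 laboratory baseline exists as a rule.** SAP 6.12.4 sets Visit 3 predose for vital signs only. Protocol 4.1 says what the site does at Visit 3. It does not say that every laboratory baseline must come from that visit. No readable text imposes the rule that would leave HbA1c without a baseline.

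**Where a laboratory baseline rule would sit.** SAP 6.12.3, Clinical Laboratory Evaluation, appears in the table of contents, and its body is blacked out. The revision history says eGFR shift analyses were added there, so methods for the other laboratory shift event were placed in that section. SAP 6.12 and 6.17 both defer to the master SAP, Version 5, for general safety methods. Text that is blacked out, or held in a parent document, cannot be counted as absent from the plan.

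**The case for a change.** The best argument for a change is that the SAP for this ISA should let a reader trace its own key safety event to a collected value. Section 6.17 was added in SAP Version 2, and an event added late should be matched to the collection schedule. For HbA1c the readable text does not show that match. One can add that some text is wrong on either reading: if the master protocol collects HbA1c, the statement in both appendices that it is particular to BP03 is inaccurate; if it does not, the shift is undefined for every participant.

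Part of this stands. The link is not visible, and a cross-reference would have saved the reader a search. The appendix label may also be loose, but that would be a clerical slip that alters no sample and no result, and the serum pregnancy test shows that the column is not an exclusive list.

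The rest does not stand. The undefined case needs every applicable schedule to omit HbA1c before dosing, and no available text says so. Nor can the event be called impossible to program when the section that would hold the programming rule is hidden. The absence of a named baseline visit is also not peculiar to HbA1c, since the QTc and eGFR events in 6.17 name none either. This is a summary list that relies on definitions given elsewhere.

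**Conclusion.** No change to the plan follows. The observations are accurate: SAP 6.17 names no baseline visit, and the BP03 schedule draws HbA1c only at Visit 7 and ED. They do not show that a baseline is missing. What is left is a detail that the study statistician would resolve by looking up the HbA1c draw in the master protocol and addendum schedules, and the laboratory baseline rule in SAP 6.12.3 or the master SAP.

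The point concerns 1 of 17 key safety events and one of the two metabolic events. It does not reach the primary analysis, and adverse events by preferred term are reported regardless.

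The conclusion assumes that a pre-dose HbA1c is collected under a parent schedule. The documents available neither confirm nor contradict this. If no schedule collected one, the shift could not be computed for any participant and the point would reopen. As it stands, adding an assay or redefining the event would answer a fault that has not been shown.

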6.11. Bioanalytical and Pharmacokinetic/Pharmacodynamic Methods	12
6.12. Safety Analyses	12
6.12.1. Extent of Exposure	13
6.12.2. Deaths, Other Serious Adverse Events, and Other Adverse Events for Review	13
6.12.3. Clinical Laboratory Evaluation	14
6.12.4. Vital Signs and Other Physical Findings	16
6.12.5. Electrocardiograms	16
6.13. Subgroup Analyses.....	16

6.14. Protocol Deviations	16
6.15. Interim Analyses and Data Monitoring	17
6.16. Planned Exploratory Analyses	17
6.17. Totality of Evidence for Safety	18
6.18. Annual Report Analyses.....	19
6.19. Clinical Trial Registry Analyses	19
7. Unblinding Plan.....	21
8. References	22
9. Appendices	23

Table of Contents

Appendix		Page
Appendix 1.	Planned Laboratory Analytes and Direction of Interest.....	24

3. Revision History

SAP Version 1 was approved prior to unblinding data for H0P-MC-BP03.

SAP Version 2 was approved prior to the final lock. Major revisions include:

- Section 5.3, the method of treatment assignment description was added to align with protocol amendment. Section 6.1, the estimand for this Intervention-Specific Appendix (ISA) was described.
- Section 6.10.2, placebo borrowing analysis from previous and ongoing studies in Chronic Pain Master Protocol (CPMP) was updated and overall mean change from baseline assessment was described.
- Section 6.12.2, additional treatment-emergent adverse events, and narratives for patients with “notable” events were updated.
- Section 6.12.3, estimated glomerular filtration rate (eGFR) shift analyses was added.
- Section 6.12.4, detailed criteria of orthostatic vital sign summaries were elaborated.
- Section 6.13, subgroup analyses were updated to align with H0P-MC-CPMP SAP version 5, and frequentist subgroup analyses were added.
- Section 6.14, ‘violations’ is replaced with ‘deviations’ for consistency across CPMP documents, and the list of important protocol deviations (IPDs) is referenced in the trial issue management plan.
- Section 6.16, planned exploratory analyses were updated, including adding frequentist mixed model for repeated measures (MMRM) as sensitivity analyses and more details of propensity score analyses; details of propensity score analyses were elaborated; exploratory placebo borrowing analyses with more types of borrowing method were added.
- Section 6.17, the totality of evidence for safety was added.

4. Study Objectives

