6.12.2. Deaths, Other Serious Adverse Events, and Other Adverse Events for Review

Treatment-emergent adverse events by preferred term will be reported.

In addition to an overall listing, additional lists by terms or organ systems of interest, including cardiovascular, thyroid, and renal functions, will be generated.

The full summary of adverse events is described in the H0P-MC-CPMP SAP. Other adverse events for review coded to Medical Dictionary for Regulatory Activities (MedDRA) terms include

- Hypothyroidism (in SMQ)
- Cardiac arrhythmias (in SMQ)
 - Arrhythmia related investigations, signs, and symptoms
 - Bradyarrhythmia terms, nonspecific
 - Cardiac arrhythmia terms, nonspecific
 - Conduction defects
 - Disorders of sinus node function
 - Supraventricular tachyarrhythmias
 - Tachyarrhythmia terms, nonspecific
 - Ventricular tachyarrhythmias
- Hypotension (in preferred MedDRA term)
 - Orthostatic hypotension
 - Blood pressure ambulatory decreased
 - Blood pressure decreased
 - Blood pressure diastolic decreased
 - Blood pressure systolic decreased
 - Blood pressure orthostatic decreased
 - Dizziness

- Dizziness exertional
- Presyncope
- Syncope
- Abnormal renal function (in MedDRA HLT)
 - Renal function analyses
 - Renal failure and impairment
- MACE (including MI and stroke)
 - Death (preferred MedDRA term)
 - Cardiac arrest (preferred MedDRA term)
 - Cardiac death (preferred MedDRA term)
 - Sudden cardiac death (preferred MedDRA term)
 - Sudden death (preferred MedDRA term)
 - Ischaemic heart disease (SMQ)
 - Ischaemic central nervous system vascular conditions (SMQ)
- Depression (in MedDRA HGLT)
 - Depressed mood disorders and disturbances
- Congestive Heart Failure (in SMQ)
 - Cardiac Failure
- Substance abuse (in MedDRA HLT)
 - Substance related and addictive disorders

Narratives will be provided for patients with the following “notable” events, in addition to the “notable” events listed in the H0P-MC-CPMP SAP.

- Treatment-emergent elevated amylase or lipase $>3x$ ULN
- Renal treatment-emergent adverse events.

CCI

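### The cystatin C eGFR key safety event in SAP Section 6.17 names no normal baseline; if normal is a band separate from mild, a fall from normal to moderate or severe is not counted

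*SAP*

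**What the plan says.** SAP Section 6.17 lists the key safety events by domain. Under renal function it gives "Treatment-emergent abnormal eGFR based on Cystatin C: Shifts", followed by two lines: "Mild at baseline to moderate/severe during the double-blind treatment period" and "Moderate at baseline to severe during the double-blind treatment period". The only other renal item is "Serious renal event". This part of the list carries no redaction mark.

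Under metabolic function, the same list words the HbA1c event as "Shift from low/normal at baseline to high at least once during the double-blind treatment period", so there the unimpaired starting category is named.

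The eGFR bands are not defined in any visible text. The SAP revision history says "Section 6.12.3, estimated glomerular filtration rate (eGFR) shift analyses was added", but the text of Section 6.12.3 is redacted. Section 6.17 also defers to the master protocol: "The totality of evidence for safety analysis has been briefly described in the H0P-MC-CPMP SAP Version 5". That SAP was not supplied.

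Protocol Section 5.2, criterion [2030], excludes participants with CKD-EPI eGFR below 60 ml/min/1.73 m² at Visit 1 or Visit 2. It does not say whether the marker is creatinine or cystatin C. Protocol Section 1.3 schedules cystatin C at Visits 3 to 7 and at early discontinuation.

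**The concern.** Mild, moderate and severe usually grade impairment, which implies a further band for no impairment. On that reading the event has no line for participants who start unimpaired. Given criterion [2030], nearly all participants should start at 60 or above. The moderate-baseline line would then apply to few of them, mainly those whose cystatin C value differs from the screening value, while the normal-baseline group has no line.

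The result would be an inconsistent count. A large fall from a normal baseline would go unrecorded, and a smaller fall from mild to a higher final value would be recorded. This is the only renal laboratory event in the Section 6.17 list. What is at stake is the completeness of one key-event count in the safety summary. The primary analysis is not touched.

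**Working it through.** The plan states no figure that depends on this point, so there is none to reproduce. The check has two parts.

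**1. Which worsening shifts are counted.** Assume four ordered bands: normal, mild, moderate, severe.

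| Shift | Counted in Section 6.17? |
|---|---|
| normal to mild | no |
| normal to moderate | no |
| normal to severe | no |
| mild to moderate | yes |
| mild to severe | yes |
| moderate to severe | yes |

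Five shifts end in moderate or severe. Three are counted; the two that start from normal are not. On a three-band scale with normal inside mild, only the last three rows exist and all are counted.

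**2. How much this could matter.** The documents give neither bands nor an eGFR distribution, so these inputs are assumptions:
- Bands: normal 90 or above, mild 60-89, moderate 30-59, severe below 30.
- Baseline cystatin C eGFR *b*: normal distribution with mean 80, 85, 90 or 95 and SD 15 or 20, with and without truncation at 60. That makes 4 × 2 × 2 = 16 settings. Both truncation options are used because criterion [2030] does not name the marker.

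By arithmetic on these bands:
- 95 to 45 is a fall of 50/95 = 52.6%: not counted.
- 85 to 42 is a fall of 43/85 = 50.6%: counted.
- 75 to 55 is a fall of 20/75 = 26.7%: counted.

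The share starting at 90 or above runs from 25.2% (mean 80, SD 15, no truncation) to 63.7% (mean 95, SD 15, truncated). That is about 50 to 127 of 200 participants.

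For a proportional fall *d*, a participant ends below 60 if *b* < 60/(1 − *d*). Define:
- N = P(90 ≤ *b* < 60/(1 − *d*)), normal to moderate or severe
- M = P(60 ≤ *b* < min(90, 60/(1 − *d*))), mild to moderate or severe
- S = P(30 ≤ *b* < min(60, 30/(1 − *d*))), moderate to severe (zero under truncation)

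The share of declines that a corrected event would count, but the present one does not, is N/(N + M + S).

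N is zero unless 60/(1 − *d*) > 90, that is, unless *d* > 1/3.

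The two extreme settings at *d* = 0.40, where the limit is 60/0.60 = 100:
- Mean 80, SD 15, no truncation: N = 0.161, M = 0.656, S = 0.022; share = 0.161/0.840 = 0.192.
- Mean 95, SD 15, truncated: N = 0.264, M = 0.363, S = 0; share = 0.264/0.627 = 0.421.

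Across the 16 settings:

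| Proportional fall | Uncounted share, minimum to maximum |
|---|---|
| 30% | 0 |
| one third | 0 |
| 35% | 6-14% |
| 40% | 19-42% |
| 45% | 24-56% |
| 50% | 25-62% |

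These are shares among declines of a given size. They do not forecast how many such declines will occur in 8 weeks.

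**The case against.** The strongest objection is that the gap depends on text nobody outside the sponsor can see. Section 6.12.3 is redacted, and it is the natural place for the bands. The SAP reference list includes two papers on eGFR equations that no visible section cites, so the hidden text very probably deals with how eGFR is derived. Only three categories are named in Section 6.17, and on a three-band scale the two lines cover every worsening. A top band of 60 and above would also fit criterion [2030]. The HbA1c contrast is weak evidence, because HbA1c is classed against a reference range and eGFR by severity grade. All of this stands, and it is why the point is conditional. A reader might infer that the plan has been shown to lose renal events, or that it fails to define its bands. The documents support neither: the first depends on unseen bands, and redacted text is not missing from the plan.

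The second objection is that little follows even on four bands. SAP Section 6.12.2 provides renal adverse event listings and narratives for "Renal treatment-emergent adverse events", Section 6.17 adds serious renal events, and the Section 6.12.3 shift analyses may show the case directly. This largely stands. However, the adverse event routes work only if someone reports an event, and a shift table would not put the case into the key-event count.

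The third objection is that falls of more than one third in 8 weeks are large, and the protocol's risk table (Section 2.3.1) names only cardiovascular and thyroid risks. This also stands and limits the expected number of cases.

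**Conclusion.** The point holds conditionally and is minor. As written, the event names no normal baseline. If normal is a separate band, shifts from normal to moderate or severe are not counted. On the assumed bands and distributions nothing is lost for falls of one third or less. Above that, the uncounted share of the declines that a corrected event would count is 6-14% at a 35% fall, 19-42% at 40% and 25-62% at 50%. If normal is inside mild, nothing is lost at any size.

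A reader might go further and add normal-to-mild shifts to the loss. That would overstate it: the event is built around arrival in moderate or severe, and the change proposed here would leave those shifts uncounted too. A reader might also infer that a safety decision could be missed. The visible text of Section 6.17 attaches no threshold, test or decision rule to this event, so that inference has no support.

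**What to change.** In SAP Section 6.17, replace the starting category of the first eGFR shift, now mild, with *normal or mild*, and leave the rest of that line and the second line as they are. If the bands already include normal in mild, the change alters no count; if they do not, it closes the gap.

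The cost is one line of SAP wording and at most one line of programming. No new data are needed, because cystatin C is already scheduled from Visit 3 to Visit 7 and at early discontinuation. The downside is that the event count may become slightly less favourable.
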